### **Outcome Measures:**

**Primary Outcome:** The primary analysis will examine, as co-primary endpoints, the percentage of participants that are *prescribed* at the end of the 12-month period: (a) the full randomized dose of metformin according to the protocol, *and* (b) at least 50% of the randomized metformin dose according to the protocol. Dose adjustments due to decreased GFR < 45 mL/min/1.73m^2 (see above) will count as the full dose because the exposure to metformin in these subjects will be equivalent to the full dose given to subjects with normal GFR.

The two proposed co-primary endpoints provide an assessment of the feasibility, in terms of safety and tolerability of metformin. These endpoints are influenced by a number of factors, including medication

intolerance (e.g., gastrointestinal symptoms), side effects (e.g., hypoglycemia), and participant drop-out or loss to follow-up. Compliance will not be considered in the co-primary endpoints because poor compliance will not trigger a reduction in the prescribed dose unless there is intolerability or an adverse safety event.

We anticipate that most participants in the metformin arm will complete the study with the prescribed full dose as randomized because they did not have a dose reduction due to side effects or intolerance. On the other hand, some participants may require a reduction in the prescribed dose due to side effects or intolerance. Participants who do not complete the study will be considered treatment failures.

The participant's prescribed dose at the end of the intervention period will be compared to the participant's randomized dose to determine if an intended dose reduction occurred. We would consider that the benchmark is achieved if: (i) at least 67% of participants in the metformin arm are prescribed the full randomized metformin dose at the end of the 12-month intervention period, *and* (ii) at least 80% of participants in the metformin arm are prescribed at least 50% of the randomized metformin dose at the end of the 12-month intervention period.

Our rationales for these benchmark cutoffs consider: (i) a potential loss to follow-up of 5% in the metformin arm, (ii) in order for a dose to be prescribed in a larger outcomes trial, the vast majority of participants who are not lost to follow-up should not require a dose reduction because of intolerance or adverse effects during this 12-month pilot study, and (iii) participants who take lower than the randomized doses may still benefit from the therapy, so long as the percentage of such participants is low in this Pilot Clinical Trial.

**Secondary (exploratory) outcomes:** (a) Change in TKV measured by MRI. **MRI Measurement of Total Kidney Volume:**

A 3.0 T Siemens system (Siemens, Malvern, PA) will be used for all studies. Renal images will be acquired in similar manner and volumetric measurements determined as described for the CRISP study. Briefly, with subjects supine on the MR table, a phased-array surface coil will be positioned with its center over the expected location of the kidneys. Scout scans will be used to locate the scan range of the entire kidneys. A stack of axial images to cover the most anterocaudal and posterocranial aspects of the kidneys will be acquired. The field-of-view (FOV) will be kept as small as possible (30-35 cm) without producing wrap-around artifacts. The first scan will cover the posterior aspect of the kidney. Neighboring image groups will be overlapped by a single 3mm slice. The correct table position will be determined. Breath-hold coronal Regular T2 scan (SSFSE/HASTE with fat sat) of the kidneys with adjusted slice thickness, 3-9 mm, i.e. the slice thickness best attainable with a single breath-hold will be obtained. No contrast agents will be used. For analysis DICOM images will be de-identified and evaluated by a single analyst, [name] using Analyze software (Analyze 9.0, Mayo Foundation, Rochester, MN). Reliability coefficients and coefficients of variation for TKV on repeatedly acquired images of individual patients will be acquired.

(b) Change in eGFR will be determined by the CKD-EPI equation using standardized serum/plasma creatinine measurements by the central laboratory of University Hospital at baseline and at 3, 6, 9 and 12 months.

**Sample Size Calculations and Statistical Analysis.** Participant characteristics will be summarized using standard descriptive statistics for all enrolled participants and, separately, by randomized group. The primary analysis of safety and tolerability will tabulate the proportions of the participants assigned to each of the 2 treatment groups who at the end of the study: (i) are prescribed the full randomized metformin dose (allowing for dose adjustments for decreased GFR), and (ii) are prescribed at least 50% of the randomized dose. The dose prescribed for each participant at the last treatment visit (Month 12) will be used to determine whether the participant completes the study on the full prescription or at least 50% of the randomized prescription. This will take into consideration any dose reductions due to adverse effects that would have occurred at the last on-treatment visit had the study continued. In further analyses, exact 90% binomial confidence intervals will be constructed for the proportions of subjects reaching each of the co-primary endpoints in each treatment group, and for differences between the proportions reaching each of the co-primary endpoints in the metformin group vs. the placebo group. In secondary analyses, exact 90% binomial confidence intervals will also be constructed for the proportions of individuals in the metformin and placebo group who: (i) reduce and/or discontinue treatment for safety reasons (e.g. hypoglycemia or increased lactic acid level); (ii) reduce and/or discontinue treatment because of medication intolerance or pill burden, and (iii) have  $\geq 80\%$  pill count compliance. These three endpoints will address the safety, medication intolerance/ pill burden, and compliance respectively for each treatment group during the intervention period. The statistical power for attaining the 67% benchmark will be 0.87 in the metformin group if the true percent prescribed the randomized dose is at least 72%. The

statistical power for attaining the 80% benchmark will be at least 0.84 in the metformin group if the true percent prescribed at least 50% of the randomized dose is at least 84%.

**Power calculation for the exploratory outcomes: a) change in TKV:** is based on findings from the Tolvaptan trial. Annual increase in TKV was 5.5% in the placebo group and 2.8% in the tolvaptan group. We plan to recruit a total expected sample size of N = 50. Assuming a similar efficacy of metformin, we will have an 80% power to detect a similar difference with  $\alpha = 0.05$  for a two-sided test; **b) change in eGFR:** is based on the sample size (N=50) and on published observational and interventional studies in ADPKD. We estimate the change in eGFR will be + 1 mL/min/1.73m^2 in the metformin group and - 4 mL/min/1.73m^2 in the placebo group during the 12-month study period. With 25 subjects in each group, an overall standard deviation of 8, and 2-tailed test with  $\alpha=0.05$ , we will have 80% power to detect this difference in eGFR change. We acknowledge that the power is limited for the proposed exploratory outcomes of TKV and eGFR, however, our primary goal is to establish the safety and tolerability of metformin in ADPKD patients. The data obtained on TKV and eGFR from this Pilot Clinical Trial will allow estimating sample size for a larger outcomes study.

**Recruitment Plans and Study Time Line.** Subject recruitment/screening will be performed in the initial 6-8 weeks and the first subjects will begin taking pills in month 3. We propose to complete measurements on the last of the 50 subjects during month 21. We will then have 3 months to complete data analysis. The University of Colorado PKD Center has contact information on approximately 500 ADPKD subjects who live in the Denver Metro Area. We have already received an IND waiver from the FDA and registered the study with our Institutional Review Board. Our PKD center has expertise and national recognition, attracting ADPKD patients for clinical studies (Please see description of the accessible population in the human subject section).

**Potential Problems and Alternative Strategies.** Although subject recruitment and retention always are challenging, we should be able to complete the study in the proposed time line given our location in the densely populated Boulder-Denver metro area. If recruitment falls short, we will then contact ADPKD patients living outside the State of Colorado. We recognize that alternative approaches exist for examining the effect of metformin in patients with ADPKD. For example, one alternative would be to undertake a larger outcomes trial to examine renal progression more definitively than in the proposed pilot investigation. However, although a large-scale clinical interventional trial will ultimately be required, a small Pilot Clinical Trial as proposed in this application is the most cost-effective approach to obtain confirmation of the study hypothesis.

**Future directions:** We anticipate that the results from this proposal will define the safety of metformin and the appropriate hard end points for a future larger trial that will culminate in therapeutic benefits of metformin for patients suffering from ADPKD. Our research team envisions a future trial testing the long-term efficacy of metformin on kidney function (i.e., 50% decrease in eGFR and progression to ESRD) against placebo.

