**Safety and tolerability of metformin in non-diabetic subjects.** Metformin has been used in women with the polycystic ovary syndrome, with or without diabetes, without significant side effects. Nausea and diarrhea may occur in 10-25% of patients but is usually transient and responds to dose reduction. **Long-term metformin administration to non-diabetic individuals** has been studied in the **Diabetes Prevention Program Outcomes Study (DPPOS)**, in which 924 subjects at risk for the development of type 2 diabetes were given metformin 850 mg twice daily for a median of 10 years. Metformin therapy reduced the development of diabetes while no significant safety issues were identified. However, these were subjects with impaired glucose tolerance; only a small study reported the safe administration of metformin (1000 mg/day) to normal-weight women with polycystic ovary syndrome who had normal glucose tolerance tests. Nothing is known about the tolerability of metformin in non-diabetic ADPKD patients, who often are very health-conscious, slim and engaged in vigorous exercise. Therefore **our primary aim is to determine the feasibility, in terms of safety and tolerability, of prescribing metformin 1000 mg twice a day in ADPKD patients with an eGFR of 50-75 mL/min/1.73m^2. Determining the safety of metformin in CKD stage 3 (eGFR 30-60 mL/min/1.73 m^2) is of particular importance**, because these individuals have usually been excluded from treatment with metformin.

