**(ii) Session 2: Baseline measurements:**

- Resting arterial blood pressure as above, complete blood count, and comprehensive metabolic panel including a serum/plasma creatinine to estimate GFR using the CKD-EPI prediction equation
- Total Kidney Volume (TKV) and Liver Volume by MRI
- Urine sample for measurement of urine protein and creatinine to estimate urine protein excretion
- Begin study treatment (metformin or placebo)
- Study participant will be given a glucometer and instructed on how to use it at home
- All participants will have the metformin or placebo provided every 3 months. Participants will be asked to return their medication dispenser for a pill count.
- Blood and urine sample will be stored for future measurement of biomarkers of ADPKD progression.

**(iii) Session 3 (Month 3, 6 and 9):** All subjects will be asked about any adverse effects, intercurrent illnesses or changes of their concomitant medications and will have safety laboratories at 3, 6 and 9 months which will include a basic metabolic panel (i.e., serum/plasma glucose and creatinine) to estimate eGFR using the CKD-EPI equation. Study participants will be required to check their morning fasting blood sugars (BS) daily for the first week of treatment, then twice weekly for the following week, and at any time if they experience a hypoglycemic symptom (i.e., sweating, lightheadedness), and keep a log of their BS values. After each dose change of metformin during the titration period (see below) they will again check their fasting BS daily for one week and then twice weekly for the following week. These results will be reviewed during scheduled telephone interviews. Women will be counseled about contraception during the study. Should a pregnancy occur, women are requested to stop taking study drug immediately and contact the study coordinator.

(iv) **Session 4 (Month 12):** Identical to Session 2, with repeat TKV.

**Rationale for age range 30-60 years.** A narrow range for inclusion age criteria will ensure: (i) that the treatment and placebo group are well balanced; and (ii) exclusion of participants older than 60 years with relatively well preserved kidney function will ensure that only ADPKD patients with more advanced disease will be included in the study. Subjects younger than age 30 years very rarely have decreased renal function.

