**Safety monitoring.** The investigative team will establish an independent Data Safety Monitoring Board (DSMB) for this study. The DSMB will include experienced nephrologists, biostatisticians and endocrinologists. In general, the anticipated gastrointestinal side effects of metformin therapy can be medically managed through adjustment of medications. If medical management is ineffective, doses of the assigned intervention will be reduced by ½ followed by discontinuation of therapy if the side effect persists. The strategies for monitoring the anticipated adverse events are:

**(i) Symptomatic or Asymptomatic Hypoglycemia (glucose < 60 mg/dL):** Study participants will be instructed on management of hypoglycemia. Once symptoms are resolved the patient will be advised to reduce the dose by 50%. If glucose remains < 60 mg/dL in subsequent measurements despite these changes, the intervention will be discontinued. Continuous monitoring of blood glucose with a glucometer will be undertaken until hypoglycemia is resolved.

**(ii) Estimated GFR < 45 mL/min/1.73m^2:** If eGFR falls below 45 ml/min/1.73m^2 and this is confirmed by a subsequent laboratory test 2 weeks later, metformin will be decreased to 1000 mg daily.

**(iii) Estimated GFR < 30 mL/min/1.73m^2:** If eGFR falls below 30 ml/min/1.73m^2 and this is confirmed by a subsequent laboratory test 2 weeks later, metformin will be stopped, according to the KDIGO and American Diabetes Association recommendations.

**(iv) Intercurrent illness:** If a research participant develops volume depletion or an acute intercurrent illness, the patient will be instructed to stop metformin until the illness has resolved. Lactic acid will be measured if suggested by symptoms or lab results (decreased CO2); if elevated, metformin will be stopped and the patient withdrawn from the study.

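### Safety and intolerance are measured only through dose changes and the Month 12 prescribed dose, so gastrointestinal effects handled without a dose cut can go uncounted by arm

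*Combined protocol and SAP*

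**What the plan says.** All references are to the combined protocol and SAP.

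- **Primary analysis** (Sample Size Calculations and Statistical Analysis). "The primary analysis of safety and tolerability will tabulate the proportions of the participants assigned to each of the 2 treatment groups" who at Month 12 are prescribed the full dose and at least half of it. Under Outcome Measures, participants who do not complete count as failures.
- **Secondary analyses** (same section). Exact 90% intervals are planned in each arm for three proportions: those who "reduce and/or discontinue treatment for safety reasons (e.g. hypoglycemia or increased lactic acid level"), those who "reduce and/or discontinue treatment because of medication intolerance or pill burden", and those with at least 80% pill-count compliance. The section then states: "These three endpoints will address the safety, medication intolerance/ pill burden, and compliance respectively for each treatment group during the intervention period".
- **Handling of symptoms.** Rationale for the metformin dosing allows a dose increase to be put off when a participant reports significant gastrointestinal symptoms. Safety monitoring puts medical management first: "If medical management is ineffective, doses of the assigned intervention will be reduced by ½ followed by discontinuation of therapy if the side effect persists".
- **Data collected.** At Months 3, 6 and 9 (Session 3 under Experimental Design) the plan reads: "All subjects will be asked about any adverse effects, intercurrent illnesses or changes of their concomitant medications and will have safety laboratories".
- **Background rate** (Significance, on safety in non-diabetic subjects). "Nausea and diarrhea may occur in 10-25% of patients but is usually transient and responds to dose reduction".

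**The concern.** Safety and tolerability are the trial's main question. The plan asks every participant about adverse effects, and it justifies the placebo arm partly by the risk that knowing the treatment would colour how side effects are perceived. It then specifies no comparison of those side effects between arms. Its stand-in for harm is a change of dose, and a change of dose is only one of the ways in which the protocol deals with symptoms.

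A participant with real nausea or diarrhoea can therefore finish as a full success on both co-primary endpoints and be absent from the intolerance endpoint. A low reported proportion would not distinguish few symptoms from symptoms that were managed without a cut. The larger trial that this pilot is meant to inform would inherit that ambiguity in its consent information, run-in and retention assumptions.

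**Working it through.** The plan states no adverse-event rate or precision for this point, so there is no figure of its own to reproduce. The stated power for the two benchmarks does not enter.

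**Step 1. Follow a gastrointestinal symptom through the protocol.** For the first and third rows, assume that the participant completes and has no other dose change.

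| Course | Intolerance endpoint | Co-primary endpoints |
|---|---|---|
| Dose increase delayed, full dose reached by Month 12 | Not counted | Success on both |
| Titration halts below the full dose | Not clearly counted, as nothing was reduced | Fails full dose; passes half dose (lowest step 2 x 500 = 1000 mg/day, 50% of 2000); cause not shown |
| Medical management, dose unchanged | Not counted | Success on both |
| Dose reduced or stopped for symptoms | Counted, pooled with pill burden | Depends on the Month 12 prescription |
| Leaves the study | Counted only if recorded as stopping for intolerance | Failure on both, cause not shown |

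Two of the five courses leave no trace in any planned proportion, and a third shows only as a lower dose.

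**Step 2. Expected number affected.** Inputs: 25 per arm (power calculation for the exploratory outcomes) and a rate of 10-25% (Significance).

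- 25 x 0.10 = 2.5
- 25 x 0.25 = 6.25

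**Step 3. What the intolerance endpoint would show.** Let s be the share of affected participants managed without a dose cut. The documents do not give s, so the values below are assumptions. Counted rate = rate x (1 - s); uncounted participants = 25 x rate x s.

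| Assumed s | Counted rate, true rate 10% to 25% | Uncounted participants of 25 |
|---|---|---|
| 25% | 7.5% to 18.8% | 0.6 to 1.6 |
| 50% | 5.0% to 12.5% | 1.3 to 3.1 |
| 75% | 2.5% to 6.3% | 1.9 to 4.7 |

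With s = 0 nothing is lost; with s = 1 every case is. The documents do not narrow that range.

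**Step 4. One illustration with the plan's own interval (exact 90%, Clopper-Pearson).** If 6 of 25 had gastrointestinal effects, the proportion is 24%, interval 11.0% to 42.0%. If only 3 of the 6 had a dose cut, the endpoint would report 3 of 25, or 12%, interval 3.4% to 28.2%. The overlap is no reassurance: the second interval describes how often the dose was changed, which is a different quantity from how often the effect occurred.

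**The case against.** The strongest reply is that the pilot deliberately defines feasibility by whether the dose can still be prescribed, and that its secondary endpoints are openly proportions with a dose change, not event rates. Silence about an adverse-event table is not a plan to withhold one. A DSMB is to be set up, and the protocol refers to a human subject section that is not part of the public document, so reporting there cannot be excluded. This stands as a limit on the claim. It does not remove the point, because the analysis section says that these endpoints address safety and intolerance, and no tabulation for the DSMB is described.

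A reader might also infer more than the text supports:

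- **That gastrointestinal effects will usually escape the count.** The sentence that calls them usually transient adds that they respond to dose reduction, which is counted. Only that they can escape is certain.
- **That dose changes are the only thing analysed.** Non-completion counts as failure in the co-primary endpoints, compliance is analysed, and creatinine from the panels is analysed as eGFR.
- **That low glucose and raised lactate are missed.** Under Safety monitoring, glucose below 60 mg/dL leads to a dose reduction and elevated lactic acid to stopping and withdrawal. Both are named as examples in the safety endpoint.
- **That a collected CO2 series is being ignored.** CO2 appears only as a prompt for measuring lactate. That the panels record it is a reasonable inference, not a statement in the plan, and lack of a by-arm CO2 analysis in a pilot of this size is not an error.
- **That pooling with pill burden makes the endpoint unreadable.** Blinded placebo participants carry the same pill burden, so comparing arms partly separates the drug effect. Splitting the endpoint is a refinement, though a cheap one.

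**Conclusion.** The point holds in a limited form. Apart from the Month 12 prescribed-dose endpoints, safety and intolerance are measured only by dose reduction or discontinuation, while the protocol allows gastrointestinal effects to be managed without either. Effects that participants will be asked about can therefore go uncounted by arm, and tolerability harm could be understated.

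The size cannot be fixed. The background rate implies about 2.5 to 6 affected metformin participants of 25, but that figure follows a discussion of polycystic ovary syndrome and is not specific to ADPKD. The uncounted share is unknown, so the figures at 25%, 50% and 75% are illustrations. To say that the harm rate is understated, or by how much, would go beyond the documents. The change is still worth making, because it bears directly on the primary question and uses data already requested.

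**What to change.** In Sample Size Calculations and Statistical Analysis:

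1. Add, by arm, the number and proportion with any adverse event and with any gastrointestinal event, whether or not the dose changed. Include delayed or halted titration for intolerance as its own line. Give exact 90% intervals for each arm and for the difference between arms. The difference intervals extend the plan, which now has them only for the co-primary endpoints.
2. Report medication intolerance and pill burden separately.

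By-arm summaries of laboratory glucose, and of CO2 if the panels record it, are optional descriptive additions.

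The cost is SAP wording and a few tables from the planned enquiries and titration records. No visit, test, sample size, dose or clinical rule changes. The downside is that the tolerability picture may look less favourable than the dose-change endpoints alone would suggest.

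### The stated power for the two co-primary benchmarks (0.87 and 0.84) is not what 25 metformin participants give: the exact values are 0.75 and 0.80, and 0.69 for meeting both

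*Combined protocol and SAP*

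**What the plan says.** The Primary Outcome text under Outcome Measures sets two benchmarks for the metformin arm at month 12. The first is that "at least 67% of participants in the metformin arm are prescribed the full randomized metformin dose". The second is that at least 80% are prescribed at least half of that dose. The two are joined by a plain conjunction: "at the end of the 12-month intervention period, *and* (ii) at least 80% of participants in the metformin arm". Participants who do not complete the study count as failures, so the denominator is everyone randomised to metformin.

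The Sample Size Calculations and Statistical Analysis section then gives one power figure per benchmark:

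- "The statistical power for attaining the 67% benchmark will be 0.87 in the metformin group". The assumed full-dose rate behind this figure is 72% or more.
- "statistical power for attaining the 80% benchmark will be at least 0.84 in the metformin group". Here the assumed rate for half the dose or more is 84% or higher.

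No arm size or formula stands beside these figures. The arm size comes from the next part of the same section, on the exploratory outcomes: "With 25 subjects in each group, an overall standard deviation of 8". It agrees with the planned total of 50 in two groups. No power is given for meeting both benchmarks.

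**The concern.** The assumed true rates lie only 5 and 4 percentage points above the benchmarks (72% against 67%, 84% against 80%). With 25 people, one participant is 4 percentage points. Powers of 0.87 and 0.84 look too high for margins of about one participant.

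These two sentences are the only operating characteristics given for the primary aim. The plan concedes limited power for kidney volume and eGFR and points to the safety and tolerability aim as the trial's main purpose. It also ties the benchmarks to whether the dose could be prescribed in a larger outcomes trial. If the chance of missing a benchmark under good tolerability is understated, a miss could be read as evidence of poor tolerability when it is partly the play of chance in a small arm.

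**Working it through.** **Inputs.** Metformin arm n = 25 (power calculation for the exploratory outcomes). Benchmarks 67% and 80%, both required, with non-completers as failures (Outcome Measures). True rates 0.72 and 0.84 (sample-size section). The plan gives these rates as minimum values. Power rises with the true rate, so the stated powers must already hold at 0.72 and 0.84.

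**Pass counts.**
- 0.67 × 25 = 16.75, so 17 are needed: 16/25 = 64% misses and 17/25 = 68% passes.
- 0.80 × 25 = 20, so 20 are needed.

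**Exact power for each benchmark**, from P(X ≥ r) = Σ C(25, k) p^k (1 − p)^(25−k), summed over k = r to 25:
- Benchmark (i): P(X ≥ 17 | p = 0.72) = 0.754, against 0.87 stated (12 points lower).
- Benchmark (ii): P(X ≥ 20 | p = 0.84) = 0.800, against 0.84 stated (4 points lower).

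**Attempts to reproduce the stated figures.**
- Other cut-offs at n = 25: P(X ≥ 16 | 0.72) = 0.866, which rounds to 0.87, but 16/25 fails the benchmark. For the second, a cut-off of 19 gives 0.908 and 20 gives 0.800; none gives 0.84.
- Normal approximation at n = 25: 0.711 and 0.707; with continuity correction, 0.782 and 0.793.
- Arms of 32 or 33, if the 65 patients mentioned under Subjects were split in two: 0.734 and 0.757, or 0.695 and 0.731.
- All 50 participants treated as one arm: 0.787 (needs 34) and 0.834 (needs 40). Rounding the first cut-off down to 33/50 gives 0.864, but 33/50 = 66% also misses 67%.
- Pass rules based on the exact 90% confidence interval at n = 25: 0.13 and 0.07 if the lower limit must reach the benchmark; 0.99 and 0.99 if only the upper limit must.
- With cut-offs rounded up correctly, no arm of 20 to 50 exceeds 0.813 for the first benchmark. The smallest arm that comes within 2 points of both stated figures is 70 (0.850 and 0.858).

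**Power for meeting both.** Anyone on the full dose is also on at least half of it, so the two counts are nested. Each participant falls into one of three classes: full dose 0.72; reduced but at least half, 0.84 − 0.72 = 0.12; failure, 1 − 0.84 = 0.16. Summing the trinomial probabilities over all outcomes with at least 17 on full dose and at least 20 on half dose or more gives 0.686.

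**True rates that the stated powers would need.** Solving P(X ≥ 17 | p) = 0.87 gives p = 0.757. Solving P(X ≥ 20 | p) = 0.84 gives p = 0.850. With those rates (classes 0.757, 0.093 and 0.150) the same trinomial sum gives a joint power of 0.789.

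**Chance of a miss at the plan's assumed rates.**
- Benchmark (i): 1 − 0.754 = 0.246, against an implied 1 − 0.87 = 0.13, a ratio of 1.9.
- Benchmark (ii): 1 − 0.800 = 0.200, against 1 − 0.84 = 0.16, a ratio of 1.25.
- Both required: 1 − 0.686 = 0.314.

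**The case against.** Several points can be made in the plan's favour.

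- *The two errors are unequal.* This stands. The first figure is 12 points too high, the second 4. Raising the second assumed rate by one point, to 85%, gives 0.838. A near doubling of the chance of failure applies only to the 67% benchmark.
- *The plan claims no joint power.* This also stands. The 0.686 contradicts no stated figure; it fills a gap. It is worth reporting because the plan's own rule requires both benchmarks.
- *The sample-size text gives no arm size for these figures, so another one may have been used.* That may explain the error, as may a cut-off of 16. The cause cannot be settled from the documents. It does not rescue the figures, because no arm size that the plan supports yields them.
- *Little hangs on the power.* The primary analysis tabulates proportions, exact 90% intervals follow, the placebo arm shows failures unrelated to metformin, and safety reductions are separated from intolerance. No estimate or interval is biased by the misstatement. These features make a misreading of a missed benchmark less likely, but they do not make the stated power correct.
- *Percentages already fix the pass counts.* This is true at n = 25. The counts 17 and 20 apply only if the arm is exactly 25.

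**Conclusion.** The concern holds. At the assumed rates of 72% and 84%, 25 metformin participants give exact power of 0.75 and 0.80, not 0.87 and 0.84. The probability of meeting both benchmarks is 0.69, so a treatment tolerated exactly as assumed would miss the combined rule about 31% of the time. The main error is in the first figure; the second is smaller.

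The conclusion rests on 25 participants in the metformin arm, benchmarks judged on the observed proportion of all randomised to it, and independent participants. The joint figure also takes both true rates exactly at their stated minimum values.

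**What to change.** In the sample-size section, state the arm size and replace the two powers with 0.75 (at least 17 of 25 when the true rate is 72%) and 0.80 (at least 20 of 25 when it is 84%). Add that the probability of meeting both is about 0.69 at those rates.

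The alternative is to keep 0.87 and 0.84 and restate the true rates they need, about 75.7% and 85.0%. The joint figure is then about 0.79, and the higher rates need a justification.

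In the Primary Outcome text, give the pass counts 17/25 and 20/25 next to the percentages, and say that they are to be recalculated from 67% and 80%, rounding up, if the arm is not exactly 25.

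The cost is a few sentences and less favourable stated figures. Sample size, endpoints, analyses and patient procedures do not change.

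### The eGFR power is stated as 80%, but the inputs given for it (difference 5, SD 8, 25 per group, two-sided 0.05) yield about 58%

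*Combined protocol and SAP*

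**What the plan says.** The calculation is part (b) of the paragraph on power for the exploratory outcomes in the combined protocol and SAP. It gives the expected effect: "We estimate the change in eGFR will be + 1 mL/min/1.73m 2 in the metformin group and - 4 mL/min/1.73m 2 in the placebo group", over the 12-month study period. It continues: "With 25 subjects in each group, an overall standard deviation of 8", with a two-tailed test at alpha 0.05, and concludes that "we will have 80% power to detect this difference in eGFR change".

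The total of 50 enters this calculation as a given and is not a result of it. The sentence that follows adds a general caveat: "We acknowledge that the power is limited for the proposed exploratory outcomes of TKV and eGFR". The caveat carries no figure.

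The section on secondary (exploratory) outcomes says that eGFR is measured "at baseline and at 3, 6, 9 and 12 months". Neither that section nor the statistical section names an analysis model for eGFR, a covariate adjustment, or a correlation between visits.

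**The concern.** The sentence states everything needed for a standard comparison of two means: difference, SD, group size, sidedness and alpha. A standardised difference of 5/8 = 0.625 with 25 per group is too small for 80% power at a two-sided 0.05, so the printed result appears not to follow from its own inputs.

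What is at stake is how the eGFR result will be read. A reader who accepts 80% would treat a non-significant difference as fairly good evidence against an effect of 5 mL/min/1.73m². If the power is nearer 58%, the same result says much less. The caveat does not settle this, because a reader who sees 80%, a conventional target, followed by a remark that power is limited cannot tell which statement to rely on.

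**Working it through.** **Inputs**, all from part (b) of the exploratory power paragraph:
- Difference in change: +1 - (-4) = 5 mL/min/1.73m²
- SD: 8
- Group size: 25 and 25
- Test: two-sided, alpha 0.05
- Stated power: 80%

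**Step 1: attempt to reproduce the 80%.** Standard error of the difference = 8 × √(2/25) = 2.263. Noncentrality = 5/2.263 = 2.210. With 48 degrees of freedom the critical value is 2.011.

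- Two-sample t-test (noncentral t): power **0.581**. A simulation of 200,000 trials gave 0.582.
- Normal approximation: Φ(2.210 - 1.960) = Φ(0.250) = **0.599**.

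Neither is close to 0.80.

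**Step 2: what 80% would require**, changing one input at a time (t-test):

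| Input changed | Stated | Needed for 80% |
|---|---|---|
| Difference | 5 | 6.47 |
| SD of change | 8 | 6.18 |
| Participants per group | 25 | 42 |

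**Step 3: other readings of the sentence** (t-test unless noted).

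| Reading | Power | Fits the text? |
|---|---|---|
| Overall SD includes the between-group spread: within-group SD = √(64 - 2.5²) = 7.60 | 0.625 | Possible |
| One-sided 0.05 (in effect the same as two-sided 0.10) | 0.703 | No, two-tailed 0.05 is stated |
| Two-sided alpha 0.20 | 0.819 | No |
| 50 per group | 0.872 | No, 25 per group is stated |
| One-sample test, n = 25 | 0.850 | No, two groups are compared |

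No reading that keeps the stated inputs reaches 80%.

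**Step 4: 8 read as the SD of single eGFR values.** This needs a correlation r between baseline and month 12. The documents give none, so r is an assumption shown over a range. For a change score, SD of change = 8 × √(2(1 - r)). For an analysis adjusted for baseline (ANCOVA), residual SD = 8 × √(1 - r²).

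| r (assumed) | SD of change | Power, change score | Residual SD, ANCOVA | Power, ANCOVA |
|---|---|---|---|---|
| 0.5 | 8.00 | 0.58 | 6.93 | 0.71 |
| 0.6 | 7.16 | 0.68 | 6.40 | 0.77 |
| 0.7 | 6.20 | 0.80 | 5.71 | 0.86 |
| 0.8 | 5.06 | 0.93 | 4.80 | 0.95 |

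The 80% is reached at r = 0.70 for the change score and at about r = 0.63 for ANCOVA. On this reading the printed figure depends entirely on a number that is not in the documents.

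**Step 5: losses.** The rationale for the primary benchmarks mentions "a potential loss to follow-up of 5% in the metformin arm". With 24 and 25 participants, noncentrality is 2.187 on 47 degrees of freedom and power is 0.572. Losses on this scale hardly matter.

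**The case against.** The best defence is that the plan does not call 8 the SD of the change and does not name the test. Eligibility is limited to eGFR 50-80; values spread evenly over that range would have an SD of 30/√12 = 8.7, which is close to 8. So 8 may be the SD at a single visit, and a correlation of about 0.70, or about 0.63 with baseline adjustment, would then give 80%. This stands as a possible explanation. It does not make the sentence right as written: the sentence concerns the change in eGFR, gives one SD, and mentions neither a correlation nor an adjusted analysis. The defect would then be an omitted assumption, and it still has to be supplied.

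The second defence is that little depends on the figure. This largely stands. The outcome is labelled exploratory, the feasibility benchmarks do not use it, and the plan says a larger trial would be sized from the data obtained, not from this power statement. The plan also warns that power is limited. That warning softens the effect on a reader of the whole paragraph, but it neither withdraws nor corrects the 80%, and it agrees better with 58%.

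It is also fair to say that the 5% loss is not an input to the eGFR calculation, and that the Subjects section already refers to 65 patients to cover screen failures and withdrawals. The 57% figure is therefore only a side check, and the conclusion does not use it.

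**Conclusion.** The stated power is wrong on the stated inputs. It is 58% by the two-sample t-test (60% by the normal approximation, 62.5% if the overall SD is taken to include the between-group spread), against 80% printed. The chance of missing the assumed effect is about 42% and not 20%.

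The 58% rests on two assumptions: that 8 is the SD of the 12-month change, and that the groups are compared without adjustment. Both are the natural reading of the text. If 8 is a single-visit SD, 80% is attainable only with a correlation that the plan does not give.

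The point is minor. It affects the interpretation of one exploratory outcome and leaves the sample size, the co-primary endpoints and their benchmarks untouched.

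**What to change.** Replace the power sentence in part (b) with one of the following.

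1. If 8 is the SD of the change: with 25 per group, SD 8 and two-sided alpha 0.05, power to detect a difference of 5 mL/min/1.73m² in eGFR change is about 58%, and the difference detectable with 80% power is about 6.5.
2. If a smaller SD of change or a baseline-adjusted analysis was intended: state the SD of change, or the single-visit SD together with the assumed correlation and its source; name the analysis; and give the power that follows.

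Either version would also agree with, or explain, the caveat that follows it. The cost is one corrected sentence and, under the first option, a less favourable figure. Enrolment, procedures and the primary outcome do not change.
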